5.2 Secondary objective

- To evaluate the safety and effectiveness of switching from DSP-5423 (tablet) to DSP-5423P.
- To evaluate the effectiveness and pharmacokinetics of DSP-5423P (40-80 mg/day) for 52-week treatment.

6. Endpoints

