Based on the approved dose of blonanserin tablet, the initial dose of DSP-5423 (tablet) was set at 8 mg/day and the dose was increased or decreased according to the maintenance dose (8-16 mg/day). Oral administration was planned after meal (in the morning and in the evening) in accordance with the approved treatment regimen of blonanserin tablet.

Since initial dose was set at 8 mg/day, it was considered necessary to determine the optimal dose

for 2 weeks. It has been reported that the treatment response assessment of antipsychotics should be performed 2 to 4 weeks after administration initiation ^{ref 11)}. Furthermore, in the clinical studies of DSP-5423 (tablets) conducted in Japan, most of the common/frequent adverse events, including akathisia, tremors, insomnia, and increased blood prolactin, have been observed in 4 weeks after administration initiation. Therefore, 6-week was set as the duration enough to collect effectiveness and safety data on DSP-5423 (tablet).

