4.3 Overall study design of clinical study

This clinical study is a multicenter, perform uncontrolled, open-label, long-term administration study consisting of two cohorts. The study schematics of clinical study are presented in Figures 1 (cohort 1) and 2 (cohort 2). Details of the study assessment and other procedures (assessment, observation, laboratory test) to be performed are presented in Tables 2 (cohort 1), 3 (cohort 2) and Chapter 11 in the protocol. In both cohorts, Day 1 is defined as the day of the initial application of DSP-5423P.

Cohort 1, consisting of DSP-5423 (tablet) treatment period and DSP-5423P treatment period, and cohort 2, consisting only of DSP-5423P treatment period, will be conducted in different subjects,

and cohort 2 will be initiated after enrollment in cohort 1 has been completed. Enrollment in cohort 1 will be terminated when the number of total subjects whose DSP-5423P treatment duration is 6 weeks or more reached 50. At the completion of enrollment in cohort 1 and at the initiation of enrollment in cohort 2, the sponsor will notify the participating study centers of that.

4.3.1 Cohort 1

Cohort 1 consists of 3 periods: DSP-5423 (tablet) treatment period (6 weeks), DSP-5423P treatment period (52 weeks) and follow-up period (1-2 weeks). Prior to initiation of DSP-5423 (tablet) treatment period, washout period (up to 4 weeks) will be arranged according to the dose of prior antipsychotics (haloperidol equivalent).

[figure not shown]
1) DSP-5423 (tablet) treatment period

DSP-5423 (tablets) will be administered orally twice daily after breakfast and evening meal for 6 weeks. The initial dose of DSP-5423 (tablet) will be 8mg/day. DSP-5423 (tablet) will be administered as flexible dose (8, 12, 16 mg/day) according to the dose adjustment criteria.

2) DSP-5423P treatment period

DSP-5423P will be applied once daily for 52 weeks. The study drug will be applied to the subject's back, chest, or abdomen. Start DSP-5423P application with the dosage according to the final dosage of DSP-5423. DSP-5423P will be applied as flexible dose (40, 60, 80 mg/day) according to the dose adjustment criteria.

Figure 1 Study schematic (cohort 1)

* If the dose of the prior antipsychotics is 12.0 mg/day or less (haloperidol equivalent), to initiate the administration of the DSP-5423 (tablet) after termination of the prior antipsychotics. Washout period may be arranged and down-titration would be done as needed prior to termination.

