7.2.1 Adverse event

In this study, relevant events occurred from the treatment initiation of DSP-5423 (tablet) to follow-up visit in cohort 1 and ones occurred from the initiation of DSP-5423P application to follow-up visit in cohort 2 will be captured as adverse events. An AE can, therefore, be any unfavorable and unintended sign (including an abnormal laboratory finding), symptom, or disease occurring after the administration of a medicinal (investigational) product, whether or not considered related to the medicinal (investigational) product.

In the cohort 1, AEs that occur during the DSP-5423 (tablet) treatment period and worsen during the DSP-5423P application period will be recorded as both AEs in the DSP-5423 (tablet) administration period and also as AEs in the DSP-5423P application period with start date as the onset date of the worsening AE. AEs that occur during the DSP-5423 (tablet) treatment period without further worsening in the DSP-5423P application period will be recorded as AEs only in the DSP-5423 (tablet) treatment period

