9.12.1 Adverse event

The adverse event will be coded using the Medical Dictionary for Regulatory Activities (MedDRA), Version 19.1. Treatment-emergent adverse event (TEAE) is defined as adverse events with start date on or after Day 1. Regardless of cohort, adverse events occurred on same date as the initial date of application of DSP-5423P will be defined as TEAE. All adverse events, regardless of TEAE or not, will be listed. A treatment-related TEAE is defined as a TEAE for which the causal relationship to the study treatment is either ‘definite’, ‘probable’, or ‘possible’.

The summary of TEAE will include the number of event, and the number and percentage of subjects which are classified in the following TEAE or treatment-related TEAE categories. Extrapyramidal (EPS) adverse event will be defined based on MedDRA PT and determined at blinded data review meeting. The skin-related adverse event will be defined as an adverse event

with any application sites collected on EDC.

- Adverse event (any TEAE)
- Death (TEAE leading to death)
- Serious adverse event (serious TEAE)
- Adverse event leading to treatment discontinuation
 - (TEAE leading to treatment discontinuation)
- Severe adverse event (severe TEAE)
- Extrapyramidal adverse event (extrapyramidal TEAE)
- Skin-related adverse event at the application site (skin related TEAE)

The number and percentage of subjects who have TEAE or treatment-related TEAE will be summarized by SOC/PT for each cohort. If a subject has multiple events categorized in same SOC/PT, the subject will be counted only one time into the SOC/PT. SOCs are sorted by alphabetically and PTs are sorted within SOC in descending order of frequency of cohort total. If there are ties, PTs are sorted by alphabetically. TEAE leading to treatment discontinuation will be summarized in the same manner.

Common TEAE are PT of TEAEs experienced by 2% or more subjects in cohort total. Common TEAE and common treatment-related TEAE will be summarized by SOC/PT.

The number and percentage of subjects who have TEAE or treatment-related TEAE will be summarized by SOC/PT and maximum severity. For this summaries, if a subject experienced more than one episode of a TEAE within a PT, the subject is counted only once in the PT at the maximum severity. If the maximum severity is missing, the episode will be kept as missing (not specified). In determining maximum severity, severities are ranked from missing (not specified), mild, moderate, to severe.

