The number and percentage of subjects who have TEAE or treatment-related TEAE will be summarized by SOC/PT and first onset date. If a subject experienced more than one event within a PT, the subject is counted only once in the PT based on the earliest event started on the same or closer to Day 1. Denominator of percentage for each period of interest is the number of subjects who were treated with DSP-5423P in each period.

Onset: Day 1 to 7, Day 8 to 14, Day 15 to 28, Day 29 to 42; Week 1 to 6;
Week 1 to 13; Week 14 to 26; Week 27 to 39; Week 40 or later
(Week 1=Day 1 to 7, Week 2=Day 8 to 14)

As TEAE of interests, Extrapyramidal TEAE and skin related TEAE will be summarized by SOC/PT. Additionally, those TEAE will be summarized by maximum severity or first onset date in same manner as summaries of TEAE. In summary tables, the frequencies for entire TEAE related to extrapyramidal symptoms or TEAE related to skin, not just by SOC/PT, will be presented.

Adverse events and extrapyramidal adverse events started during DSP-5423(tablet) treatment period of Cohort 1, meaning Tab-Day 1 to Day -1 will be summarized by SOC/PT.

Listings for adverse events, AE leading to death, SAE, AE leading to treatment discontinuation, Extrapiramidal AE and skin related AE will be generated. Both TEAE and pre-treatment event which started before Day 1, will be included in those listings. In the listing for skin related AE, the application site will also be presented.

The adverse events during DSP-5423(tablet) treatment period of Cohort 1 will be listed.

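### Cohort 1's adverse event tables cannot isolate the tablet-to-patch switch: tablet onsets form one undivided six-week count, and events carried over unworsened appear in no patch-phase AE table

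*SAP*

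**What the plan says.** - **Objective.** Protocol 5.2 includes "To evaluate the safety and effectiveness of switching from DSP-5423 (tablet) to DSP-5423P". The study is uncontrolled and has no arm that stays on tablets. Cohort 1 takes tablets for 6 weeks and then the patch for 52.
- **Tablet-phase events.** SAP 9.12.1: "Adverse events and extrapyramidal adverse events started during DSP-5423(tablet) treatment period of Cohort 1, meaning Tab-Day 1 to Day -1 will be summarized by SOC/PT". These are Tables 14.3.1.21 and 14.3.1.22, in all subjects treated with tablet, with no split by time of onset.
- **Patch-phase events.** SAP 9.12.1: "Treatment-emergent adverse event (TEAE) is defined as adverse events with start date on or after Day 1", where Day 1 is the first patch. They are also tabulated by first onset ("Onset: Day 1 to 7, Day 8 to 14, Day 15 to 28, Day 29 to 42; Week 1 to 6", then later windows). The denominator for each window is the subjects on patch in that window.
- **Events that cross the switch.** SAP 7.2.1: "AEs that occur during the DSP-5423 (tablet) treatment period without further worsening in the DSP-5423P application period will be recorded as AEs only in the" tablet period. An event that worsens on patch is recorded in both periods, with the date of worsening as its patch-phase onset. Protocol 12.1.1 has the same rule.
- **Timing.** Protocol 7.2.2, on earlier Japanese tablet studies: "most of the common/frequent adverse events, including akathisia, tremors, insomnia, and increased blood prolactin, have been observed in 4 weeks after administration initiation".

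**The concern.** The switching question is whether adverse events change when the same active ingredient moves from tablet to patch. A reader of the AE tables has one tablet figure to set beside the patch figures. The patch column that matches it in length is Week 1 to 6. For a subject who started blonanserin in the study, that column covers weeks 7 to 12 of the drug, while the tablet figure covers weeks 1 to 6 and so contains the early peak.

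An event that starts on tablet and continues unchanged also counts against the tablet alone, however long it lasts on patch. For early-onset events such as akathisia, tremor and insomnia, both features lower the patch figure relative to the tablet figure with no formulation difference. The main patch tables cover 52 weeks against 6, which pushes the other way for events that keep arising at a steady rate. The planned AE tables therefore mix the effect of the switch with time since starting the drug and with window length.

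**Working it through.** **The plan's own figure.** The only computable planning number is enrolment: 100 subjects with 52 weeks' exposure and about half terminating early gives 100 / (1 − 0.5) = 200. It reproduces and does not bear on this point.

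**Inputs from the documents.** Tablet phase 6 weeks; patch phase 52 weeks; most common events within 4 weeks of starting; the counting rules above. No AE rates or onset shares are given.

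**Assumptions (not in the documents).** The formulations are identical. The hazard of first onset depends only on weeks since starting blonanserin, with one constant value in weeks 0–4 and another in weeks 4–58. *P* is the 58-week cumulative incidence, and *s* is the share of the 58-week cumulative hazard in weeks 0–4. Of subjects with a tablet-phase event, 50% persist unworsened (not counted on patch), 10% worsen (counted at once) and 40% resolve and are at risk again. Patch dropout is exponential, 50% over 52 weeks.

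**Formulas.**
- H = −ln(1 − P)
- Late weekly hazard h = (1 − s)H / 54
- Tablet T = 1 − exp(−(sH + 2h))
- Dropout hazard d = ln 2 / 52 = 0.0133 per week
- New onset within w patch weeks: q(w) = [h/(h + d)] × [1 − exp(−(h + d)w)]
- Patch figure = 0.1T + (1 − T + 0.4T) × q(w)

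**Worked case, P = 30%, s = 0.75.** H = 0.3567 and h = 0.00165. T = 1 − exp(−0.2708) = 23.7%. q(6) = 0.95% and q(52) = 5.96%. Subjects at risk on patch: 0.763 + 0.095 = 0.858.
- Patch Week 1 to 6: 2.37% + 0.858 × 0.95% = 3.2%, ratio 0.13.
- Patch 52 weeks: 2.37% + 0.858 × 5.96% = 7.5%, ratio 0.32.

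**Range at P = 30%, 50% dropout.**

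| s | Tablet 6 wk | Patch Wk 1–6 | Patch 52 wk |
|---|---|---|---|
| 0.60 | 19.7% | 3.3% | 10.2% |
| 0.75 | 23.7% | 3.2% | 7.5% |
| 0.90 | 27.6% | 3.1% | 4.8% |
| 4/58 (constant) | 3.6% | 3.8% | 20.0% |

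- For s from 0.60 to 0.90 the Week 1 to 6 ratio is 0.11–0.17 at every P tried from 10% to 80%.
- Over the persist/worsen mixes tried at P = 30% it is 0.01–0.56. With neither persistence nor worsening it is 0.01–0.08, so early onset drives most of the effect.
- With constant onset the 52-week patch figure is 5.5 times the tablet figure, or 7.5 times with no dropout (27.1% against 3.6%).
- The 52-week patch and 6-week tablet figures break even at s = 0.31–0.42 with 50% dropout and 0.39–0.50 with none.

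**Sensitivity to what the protocol's "most" covers.** Suppose a share f of first onsets over L weeks falls in weeks 1–4, the rest is uniform, and the later rate continues through week 12. Then the ratio is [6(1 − f)/(L − 4)] / [f + 2(1 − f)/(L − 4)]. For L = 8 it is 1.00 (f = 0.5), 0.75 (f = 0.6) and 0.33 (f = 0.8). For L = 58 it is 0.11 (f = 0.5) to 0.03 (f = 0.8).

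**The case against.** The strongest reply is that the SAP specifies no tablet-versus-patch AE contrast. The tablet tables are separate descriptive displays in a different population, and pairing them with a patch column is the reader's act. That stands: no planned analysis is wrong. But descriptive tables are the whole safety analysis here, and these are the AE tables available for the switching objective.

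Other parts of the reply also stand:
- A reader might infer that the patch will look safer in general. The documents do not support that. Steady-onset events look worse on patch in the 52-week tables, and worsened events are counted on patch.
- Not every subject is new to blonanserin. Exclusion criterion 15 bars only recent users judged resistant, and SAP 9.11.4 stratifies by prior blonanserin. The early-peak argument is weaker for prior users.
- Events are queried in the same way at all visits (Protocol 11.3.1). The difference lies in tabulation, not ascertainment.
- Much is already shown over time. DIEPSS is summarised by visit in both phases and plotted across both (SAP 9.12.5). Antiparkinson use has an overall tablet figure, a Day -1 column and patch windows, repeated in subjects not using it at Day -1 (SAP 9.7). Laboratory values, including prolactin, are given by visit in both phases. Extrapyramidal TEAEs have early patch windows (Table 14.3.1.25). It would be too strong to say that a rise at the switch is hidden.
- Cohort 2's first six patch weeks are aligned on time since starting study treatment, but that cohort is non-randomised, enrolled later and makes no switch.

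A reader might extend the point to the pooled rule that "Common TEAE are PT of TEAEs experienced by 2% or more subjects in cohort total". That does not follow: SOC/PT tables by cohort report every term, so the cut affects display only.

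**Conclusion.** The point holds in a limited form. Cohort 1's AE and extrapyramidal AE tables do not separate the switch from time since starting blonanserin or from window length, and events carried over unworsened are in no patch-phase AE table. With identical formulations, early-onset events in newly started subjects would favour the patch when the tablet total is read beside patch Week 1 to 6. Steady-onset events would favour the tablet when it is read beside the 52-week total.

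The structure comes from the documents; the sizes do not. Ratios from 0.01 to 1.00 for the first reading, and 5.5 to 7.5 for the second at P = 30%, rest on assumed onset shares, persistence and dropout. The protocol's statement on timing gives no percentage and concerns earlier studies of unstated length. Because the other time-resolved measures cover part of the gap and no formal comparison is planned, this is an optional improvement (COULD), not a defect that undermines the study.

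**What to change.** In SAP 9.12.1:

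(a) Split Tables 14.3.1.21 and 14.3.1.22 by onset at Tab-Day 1–7, 8–14, 15–28 and 29 to Day -1. The denominator should be subjects treated with tablet in each window, mirroring the patch rule. State that switching safety in Cohort 1 is read from Tab-Day 29 to Day -1 against patch Day 1–7, 8–14 and 15–28, and not from the six-week tablet total against patch Week 1 to 6 or the 52-week total. Any version limited to subjects who went on to apply the patch should be supplementary only, because it removes those who stopped for late-tablet events and so tilts against the patch.

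(b) Add to the Cohort 1 patch-phase AE and extrapyramidal AE tables a row for subjects with a tablet-onset event ongoing on Day 1, with its outcome.

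**Cost.** SAP wording and a few table columns and rows, from onset, end and outcome data already collected.

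**Downsides.** Cells will be small. Visit frequency differs: tablet weeks 5–6 have one scheduled visit, at Week 6, while the first two patch weeks have visits at Weeks 1 and 2. First-onset counting restarts at Day 1, so a recurrence can count on patch without counting in the late-tablet window. Early patch extrapyramidal counts overlap the antiparkinson taper in Protocol 10.3.3.2 and should carry a footnote saying so.

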9.12.2 Laboratory test

Observed values and changes from baseline at DSP-5423P application period for the hematology, and blood chemistry parameters will be summarized by visits including LOCF endpoints. For urinalysis parameters, the number and percentage of subjects in each category of parameters will be summarized at baseline of DSP-5423P application period, each visit, and LOCF endpoint. All laboratory parameters and any abnormal laboratory values, which are all values beyond its own normal range at least one time whenever in DSP-5423P application period, will be listed respectively.

Criteria for Markedly Abnormal Post-Baseline Laboratory Values(MAPLV) for abnormal values in the hematology, and blood chemistry parameter can be found in Table 6. The frequencies and percentages of subjects who met MAPLV at least once in the post-baseline of DSP-5423P (including unscheduled visits), will be presented.

Table 6 Criteria for Markedly Abnormal Post-Baseline Laboratory Values

Hematology Parameter	Markedly Abnormal Range
Hemoglobin	Male: ≤ 11.5 g/dL
	Female: ≤ 9.5 g/dL
Hematocrit	Male: $\leq 37\%$
	Female: $\leq 32\%$
WBC	$\leq 2.8 \times 10^3/\mu\text{L}$
	$\geq 16 \times 10^3/\mu\text{L}$
Platelets	$\leq 75 \times 10^3/\mu\text{L}$
	$\geq 700 \times 10^3/\mu\text{L}$
Chemistry Parameter	Markedly Abnormal Range
ALT	$\geq 3 \times \text{ULN}$
AST	$\geq 3 \times \text{ULN}$
Alkaline Phosphatase	$\geq 1.5 \times \text{ULN}$
Na/Sodium	$\leq 130 \text{ mEq/L}$

	> 150 mEq/L
K/Potassium	< 3 mEq/L
	> 5.5 mEq/L
Cl/Chloride	< 90 mEq/L
	> 115 mEq/L
Blood Glucose (fasting)	< 50 mg/dL
	> 250 mg/dL
HbA1c	>= 7.5%
Total Bilirubin	> 2 x ULN
Blood Urea Nitrogen	> 30 mg/dL
Creatinine	> 2.0 mg/dL
CK	> 3 x ULN
Serum Prolactin	>= 5 x ULN
Triglycerides (fasting)	> 300 mg/dL
Total Cholesterol (fasting)	> 300 mg/dL

Note: A value is considered MAPLV if it is outside the Markedly Abnormal Range.

Note: Blood glucose, triglycerides, and total cholesterol are limited for blood samples collected in fasting state.

Box plot of observed value of the hematology and blood chemistry parameters will be provided by visits including baseline of DSP-5423P application period and LOCF endpoint.

For DSP-5423(tablet) treatment period in Cohort 1, observed values and changes from baseline at DSP-5423(tablet) treatment period for the hematology, and blood chemistry parameters will be summarized by visits including LOCF endpoints. For urinalysis parameters, the number and percentage of subjects in each category of parameters will be summarized at baseline of DSP-5423(tablet) treatment period, each visit, and LOCF endpoint. Box plot of observed value of the hematology and blood chemistry parameters will be provided by visits including baseline of DSP-5423(tablet) treatment period.

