Body temperature, blood pressure, pulse rate		X	X ^{d)}	X	X	X	X ^{e)}	X	X	X	X	X	X	X	X	X	X	X	X	X	X	X	
Adverse event monitoring			←																			→	
Blood sampling for PK					X		X ^{e)}			X							X			X	X		
Questionnaire																				X	X		

- a) Tab-Day 1 is defined as the day of the initial administration of DSP-5423 (tablet), and Day 1 is defined as the day of the initial application of DSP-5423P.
- b) At Visit 2 (before administration initiation of DSP-5423 (tablet)), Visit 6 (the end of DSP-5423 (tablet) treatment phase) and Visit 113 (the end of DSP-5423P treatment phase), blood samples will be collected under fasting conditions (at least 10 hours after the last meal). At other visits, blood samples should be collected under fasting conditions (at least 10 hours after the last meal) whenever possible.
- c) To be performed only in female subjects who are premenopausal and of childbearing potential.
- d) Must be performed before the beginning of treatment with DSP-5423 (tablet). For the subject treated with any antipsychotic, must be performed after discontinuation of antipsychotics and before the beginning of treatment with DSP-5423 (tablet).
- e) Must be performed before the beginning of treatment with DSP-5423P.
- f) If the subject discontinues the study drug during the DSP-5423 (tablet) treatment phase, the subject will undergo the following safety assessments: study treatment compliance, DIEPSS, C-SSRS, laboratory test, pregnancy test, 12-lead ECG, body weight, body temperature, blood pressure, pulse rate, and adverse event monitoring at the discontinuation visit.
- g) Must be performed before the initiation of post-treatment with antipsychotics excluding the study drug.

Table 3 Schedule of Assessments (Cohort 2)

		DSP-5423P treatment phase (52 weeks)															Discontinuation	Follow-up phase (1-2 weeks)	
Visit No.	-	1	2	101	102	103	104	105	106	107	108	109	110	111	112	113			
Timeline from initiation of DSP-5423P application	-	Screening	Baseline	Week 1	Week 2	Week 4	Week 6	Week 8	Week 12	Week 16	Week 20	Week 24	Week 28	Week 36	Week 44	Week 52			
Visit window (Day)		-28-	-2-1	5-11	12-18	26-32	40-46	54-60	78-92	106-120	134-148	162-176	190-204	239-267	295-323	351-379	At discontinuation +5	6~17 days after completion of treatment or discontinuation	
Obtaining informed consent	X																		
Patient demographics and medical history	X																		
Dispense study drug		X ^{a)}	X	X	X	X	X	X	X	X	X	X	X	X	X				

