11.3.5 Clinical Laboratory Tests

Blood and urine samples will be collected for clinical laboratory tests. The Investigators will record the date of collection and whether or not the subject is under fasting conditions (at least 10 hours after the last meal) in the CRFs. All clinical laboratory tests will be performed centrally.

The clinical laboratory tests required by the protocol are listed in Table 15. Detailed instructions regarding clinical laboratory procedures, sampling, shipping, and reporting can refer to the instructions manual provided by the Sponsor.

Table 14 Contents of laboratory variables

Hematology	white blood cell count, red blood cell count, hemoglobin, hematocrit, platelet count, differential white blood cell count (neutrophils, eosinophils, basophils, monocytes, and lymphocytes)
Blood biochemistry	total protein, total bilirubin, AST, ALT, ALP, γ -GTP, LDH, total cholesterol, triglycerides, BUN, creatinine, CK, Na, K, Cl, blood glucose, HbA1c, serum prolactin
Urinalysis (Qualitative)	glucose, protein, occult blood, urobilinogen
Pregnancy test (premenopausal women of childbearing potential only)	urine chorionic gonadotropin

Guidance for Blood Sample Collection

Blood samples will be collected under fasting conditions (at least 10 hours after the last meal) at Visit 2 (before beginning of study drug administration/application in the cohort 1 and the cohort 2 each), Visit 6 of the cohort 1 (end of the DSP-5423 (tablet) administration) and Visit 113 (end of the

DSP-5423P application in the cohort 1 and cohort 2 each). At other visits, blood samples should be collected under fasting conditions, whenever possible.

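### By-visit and LOCF changes in glucose, triglycerides and total cholesterol can set fasting baselines against non-fasting samples, because the SAP uses the recorded fasting status only in Table 6

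*SAP*

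**What the plan says.** Protocol 11.3.5 makes fasting compulsory at three visits. The first is before study drug starts in either cohort: "Blood samples will be collected under fasting conditions (at least 10 hours after the last meal) at Visit 2". The others are Visit 6 in cohort 1 (end of the tablet period) and Visit 113 in both cohorts (Week 52). For the rest it says: "At other visits, blood samples should be collected under fasting conditions, whenever possible". The footnotes to the schedules in Protocol Tables 2 and 3 repeat this rule. Investigators also record "whether or not the subject is under fasting conditions (at least 10 hours after the last meal) in the CRFs", so each collection carries a fasting flag.

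For the patch period, SAP 9.12.2 plans that "Observed values and changes from baseline at DSP-5423P application period for the hematology, and blood chemistry parameters will be summarized by visits", including LOCF, with box plots of the observed values. For the cohort 1 tablet period, "observed values and changes from baseline at DSP-5423(tablet) treatment period for the hematology, and blood chemistry parameters will be summarized by visits", again with LOCF and box plots. None of these outputs has a fasting condition. The only restriction is in Table 6 (markedly abnormal values), where the three rows are labelled as fasting and a note adds: "Blood glucose, triglycerides, and total cholesterol are limited for blood samples collected in fasting state".

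No other section supplies the missing condition:
- SAP 8.1 requires only that a subject has both a baseline and a visit value.
- SAP 8.4 (baseline), 8.5 (visit mapping) and 8.6 (LOCF) do not mention fasting.
- SAP 10.2 lists one blood chemistry table per treatment phase and no fasting version.

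**The concern.** Safety over 52 weeks is the primary objective, and laboratory values are a safety endpoint. The study has no control arm, so a sampling artefact has no parallel group in which to cancel. Change from baseline is the evidence.

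The fasting rule is strict at the two ends of the patch phase and looser in between. If some interim samples are taken after a meal, the tables could show a mid-study rise in glucose or triglycerides that falls back at Week 52, with no drug effect at all. Subjects who leave early have a discontinuation sample for which fasting is not compulsory, and that sample can become their LOCF value.

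Section 9.12.2 also treats the same three analytes in two ways. Its counts of markedly abnormal values use fasting samples only, while its means, changes and box plots use every sample. A reader could not reconcile the two.

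**Working it through.** The plan gives no figure on this point, so there is none to reproduce. The check has two parts: a count of exposed visits and a simple mixture calculation.

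**Step 1: which time points require fasting** (Protocol 11.3.5 and schedule footnotes; laboratory visits from SAP 8.5)

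| Time point | Fasting |
|---|---|
| Visit 2 (tablet baseline in cohort 1, patch baseline in cohort 2) | compulsory |
| Tab-Week 2 (cohort 1) | requested |
| Visit 6 (patch baseline in cohort 1) | compulsory |
| Weeks 2, 6, 12, 20, 28, 36, 44 | requested |
| Visit 113 (Week 52) | compulsory |
| Discontinuation visit | requested, as one of the other visits |

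There are 8 scheduled patch-phase laboratory visits and 1 requires fasting, so 8 − 1 = 7 do not. The observed Week 52 row is not purely completers either: SAP 8.5 maps discontinuation samples from Day 324 onward to Week 52.

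**Step 2: bias in a mean change**

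Let f_post and f_base be the non-fasting shares at the visit and at baseline, and D the fed-minus-fasting difference. If fasting status is unrelated to the drug's effect,

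bias = (f_post − f_base) × D.

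The documents give none of these three inputs. The values below are assumptions, with f_base = 0.

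| f_post | D = 10 mg/dL | D = 20 mg/dL | D = 40 mg/dL |
|---|---|---|---|
| 5% | +0.5 | +1 | +2 |
| 10% | +1 | +2 | +4 |
| 30% | +3 | +6 | +12 |
| 50% | +5 | +10 | +20 |

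If D = 0, or if f_post = f_base, the bias is 0.

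**Step 3: the baseline is not guaranteed to be fasting**

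SAP 8.4 takes the last non-missing value on or before Day 1. If the Visit 2 sample is missing in cohort 2, a screening sample can stand in. If the Visit 6 sample is missing in cohort 1, the Tab-Week 2 sample can. Neither has to be fasting. With f_base = 10%, f_post = 5% and D = 20, the bias is (0.05 − 0.10) × 20 = −1 mg/dL, so the sign can reverse.

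**Step 4: LOCF**

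Take completers' Week 52 samples and all baselines as fasting, and let d be the share leaving early. The non-fasting share at LOCF is then d × f. Protocol 15.1 reports that about half of enrolled subjects left early in previous tablet studies. With d = 0.5 and an assumed f = 0.30, the share is 0.15, and at D = 20 the bias is 0.15 × 20 = +3 mg/dL. With d = 0.3 it is 0.09 × 20 = +1.8 mg/dL; with d = 0.6 it is 0.18 × 20 = +3.6 mg/dL.

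**Step 5: after the fix**

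With fasting samples only at both time points, f_post = f_base = 0 and the bias is 0 for any D.

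**The case against.** A reader might infer that the by-visit changes are certainly biased upward for all three analytes. The documents do not support that. They give neither the non-fasting share nor the fed-minus-fasting difference, and sites are told to obtain fasting samples at every visit if they can, so the share may be very small. The baseline has no fasting filter, so the direction is not fixed. Nothing in the documents indicates a size or direction for total cholesterol.

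A reader might also infer that no fasting rule covers the discontinuation visit. It falls under the general request for other visits. Protocol 10.3.1 even places the number Visit 113 beside it, which would make fasting compulsory there. However, Protocol 10.3.2 and 10.3.3.1 give that number to the last visit only, and the schedules put discontinuation in a separate column. The better reading is that fasting is requested but not required.

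Several safeguards already exist. Completers' Week 52 samples must be fasting, which protects the comparison closest to the primary objective. HbA1c is in the same panel and carries no fasting label in Table 6, which helps for glucose but not for lipids. The markedly abnormal counts use fasting samples, and all values are listed. Table 6 applies absolute thresholds, so its fasting limit does not prove that the sponsor thinks non-fasting values unusable for mean changes. The one-half early-termination figure concerns enrolled subjects in earlier studies, whereas the population here is patch-treated subjects.

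These points limit the size and certainty of the bias. They do not close the gap: the flag is collected, one table uses it, and the other summaries of the same analytes ignore it.

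**Conclusion.** The point holds as a possible bias of unknown size. Changes in glucose, triglycerides and total cholesterol may be distorted at Weeks 2, 6, 12, 20, 28, 36 and 44, where discontinuation samples are mapped to scheduled visits, at LOCF and at Tab-Week 2. For glucose and triglycerides the direction is probably upward, on two assumptions: that fed values run higher than fasting ones, and that baseline samples are fasting more often than later ones. For total cholesterol no direction is claimed.

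The effect could be near zero. Over the assumed ranges with an all-fasting baseline it runs from 0 to +20 mg/dL at an interim visit, and it is smaller at LOCF because completers contribute fasting samples. Week 52 in completers is a like-with-like comparison. The change is worth making because the study is uncontrolled and the remedy uses data already collected.

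**What to change.** In SAP 9.12.2, specify that for blood glucose, triglycerides and total cholesterol the by-visit observed values, changes from baseline, LOCF summaries and box plots use only samples flagged as fasting on the CRF, at both baseline and the post-baseline time point, in the patch and tablet periods. LOCF for these analytes is then the last fasting post-baseline value. Keep the all-sample summaries as supplementary, or stratify them by fasting status, and report the number of non-fasting samples at each visit so that readers can judge the exposure. Add the matching titles to SAP 10.2. Listings stay complete.

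No new data are needed. The cost is fewer subjects at some visits. A fasting-only LOCF may also drop some discontinuation samples from early leavers and use an earlier time point than the rest of the panel; the supplementary all-sample table covers that loss.
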